# 8.4.2 Method of Detecting AEs, SAEs, and Other Reportable Safety Events

Care will be taken not to introduce bias when detecting AEs and/or SAEs and other reportable safety events. Open-ended and nonleading verbal questioning of the participant is the preferred method to inquire about AE occurrence.

## 8.4.3 Follow-up of AE, SAE, and Other Reportable Safety Event Information

After the initial AE/SAE report, the investigator is required to proactively follow each participant at subsequent visits/contacts. All AEs, SAEs, and other reportable safety events, including pregnancy and exposure during breastfeeding, ECIs, cancer, and overdose will be followed until resolution, stabilization, until the event is otherwise explained, or the participant is lost to follow-up (as defined in Section 7.3). In addition, the investigator will make every attempt to follow all nonserious AEs that occur in allocated participants for outcome. Further information on follow-up procedures is given in Appendix 3.

# 8.4.4 Regulatory Reporting Requirements for SAE

Prompt notification (within 24 hours) by the investigator to the Sponsor of SAE is essential so that legal obligations and ethical responsibilities towards the safety of participants and the safety of a study intervention under clinical investigation are met.

The Sponsor has a legal responsibility to notify both the local regulatory authority and other regulatory agencies about the safety of a study intervention under clinical investigation. The Sponsor will comply with country-specific regulatory requirements and global laws and regulations relating to safety reporting to regulatory authorities, IRB/IECs, and investigators.

Investigator safety reports must be prepared for SUSARs according to local regulatory requirements and Sponsor policy and forwarded to investigators as necessary.

An investigator who receives an investigator safety report describing an SAE or other specific safety information (eg, summary or listing of SAE) from the Sponsor will file it along with the IB and will notify the IRB/IEC, if appropriate according to local requirements.

# 8.4.5 Pregnancy and Exposure During Breastfeeding

Although pregnancy and infant exposure during breastfeeding are not considered AEs, any pregnancy or infant exposure during breastfeeding in a participant (spontaneously reported to the investigator or their designee) that occurs during the study are reportable to the Sponsor.

All reported pregnancies must be followed to the completion/termination of the pregnancy.

Any pregnancy complication will be reported as an AE or SAE.

The medical reason (example: maternal health or fetal disease) for an elective termination of a pregnancy will be reported as an AE or SAE. Prenatal testing showing fetus will be born with severe abnormalities/congenital anomalies that leads to an elective termination of a pregnancy will be reported as an SAE for the fetus.

Pregnancy outcomes of ectopic pregnancy, spontaneous abortion, missed abortion, benign hydatidiform mole, blighted ovum, fetal death, intrauterine death, miscarriage, and stillbirth must be reported as serious events (Important Medical Events). If the pregnancy continues to term, the outcome (health of infant) must also be reported.

# 8.4.6 Disease-related Events and/or Disease-related Outcomes Not Qualifying as AEs or SAEs

Progression of the cancer under study is not considered a reportable event unless it results in hospitalization or death.

#### 8.4.7 Events of Clinical Interest

Selected serious and nonserious AEs are also known as ECIs and must be reported to the Sponsor.

Events of clinical interest for this study include:

- 3. An overdose of Sponsor's product, as defined in Section 8.5.
- 4. An elevated AST or ALT laboratory value that is greater than or equal to 3X the ULN and an elevated total bilirubin laboratory value that is greater than or equal to 2X the ULN and, at the same time, an alkaline phosphatase laboratory value that is less than 2X the ULN, as determined by way of protocol-specified laboratory testing or unscheduled laboratory testing.\*

\*Note: These criteria are based on available regulatory guidance documents. The purpose of the criteria is to specify a threshold of abnormal hepatic tests that may require an additional evaluation for an underlying etiology. The study-site guidance for assessment and follow up of these criteria can be found in the Investigator Study File Binder (or equivalent).

### **8.5** Treatment of Overdose

For purposes of this study, an overdose will be defined as any dose exceeding the prescribed dose for MK-1088 by  $\geq$ 20% of the indicated dose. No specific information is available on the treatment of overdose of MK-1088. In the event of overdose, MK-1088 may be discontinued and the participant should be observed closely for signs of toxicity. Appropriate supportive treatment should be provided if clinically indicated.

No specific information is available on the treatment of overdose of pembrolizumab. In the event of overdose, the participant should be observed closely for signs of toxicity. Appropriate supportive treatment should be provided if clinically indicated.

### 8.6 Pharmacokinetics

To further evaluate MK-1088 exposure in this indication, and also to evaluate exposure of the proposed dosing regimen, sample collections for analysis of PK are currently planned as shown in Section 1.3. Blood samples will be obtained to measure PK of serum MK-1088. The MK-1088 serum  $C_{max}$  and  $C_{min}$  at planned visits and times will be summarized. Blood samples collected may be stored and further analysis may be performed, if required.

94

PRODUCT: MK-1088
PROTOCOL/AMENDMENT NO.: 002-01

On the day(s) of sample collection, participants must not take study medication until the predose PK and biomarker (Section 8.8) sample collections are complete. Every effort should be taken by the investigative center to document the time of the last MK-1088 dose (ie, at home) before PK collection.

## 8.6.1 Blood Collection for Plasma MK-1088

Sample collection, storage, and shipment instructions for plasma samples will be provided in the Operations/Laboratory Manual.

Pharmacokinetic samples should be drawn according to the PK collection schedule for all participants. Every effort should be taken to collect samples at 30 days after end-of-study intervention.

# 8.7 Pharmacodynamics

Pharmacodynamic parameters will not be evaluated in this study.

#### 8.8 Biomarkers

To identify novel biomarkers, the following biospecimens to support exploratory analyses of cellular components (eg, protein, RNA, DNA, metabolites) and other circulating molecules will be collected from all participants in this study as specified in the SoA:

- Blood (DNA) for genetic analysis
- Blood for serum biomarker analyses
- Blood for RNA analyses
- Archival or newly obtained tumor tissue

Sample collection, storage and shipment instructions for the exploratory biomarker specimens will be provided in the laboratory manual.

# 8.8.1 Planned Genetic Analysis Sample Collection

Sample collection, storage, and shipment instructions for planned genetic analysis samples will be provided in the Procedures Manual. Samples should be collected for planned analysis of associations between genetic variants in germline/tumor DNA and drug response. If a documented law or regulation prohibits (or local IRB/IEC does not approve) sample collection for these purposes, then such samples should not be collected at the corresponding sites. Leftover DNA extracted from planned genetic analysis samples will be stored for FBR only if participant signs the FBR consent.

# 8.9 Future Biomedical Research Sample Collection

If the participant provides documented informed consent for FBR, the following specimens will be obtained as part of FBR:

Leftover samples listed in Section 8.8

## 8.10 Health Economics Medical Resource Utilization and Health Economics

This section is not applicable.

# 8.11 Visit Requirements

Visit requirements are outlined in Section 1.3. Specific procedure-related details are provided in Section 8.

# 8.11.1 Screening

Approximately 28 days before treatment allocation, potential participants will be evaluated to determine that they fulfill the entry requirements as set forth in Section 1.3. Screening procedures may be repeated after consultation with the Sponsor.

Documented informed consent must be provided before performing any protocol-specific procedure. Results of a test performed before the participant signing consent as part of routine clinical management are acceptable in lieu of a screening test if performed within the specified time frame. Screening procedures are to be completed within 28 days before the first dose of study intervention.

## 8.11.2 Treatment Period/Vaccination Visit

Visit requirements are outlined in the SoA (Section 1.3). Specific procedure-related details are provided above in Section 8..

## 8.11.3 Discontinued Participants Continuing to be Monitored in the Study

The Discontinuation Visit should occur at the time study intervention is discontinued for any reason. If the Discontinuation Visit occurs 30 days from the last dose of study intervention, at the time of the mandatory Safety Follow-up Visit, the Discontinuation Visit procedures and any additional Safety Follow-up procedures should be performed. Visit requirements are outlined in Section 1.3. Additional details regarding participant withdrawal and discontinuation are presented in Section 7.

## 8.11.4 Posttreatment Visit

Participants will be required to return to the clinic approximately 30 days after the last dose of study intervention for the poststudy visit. If the poststudy visit occurs less than 30 days after the last dose of study intervention, a subsequent follow-up telephone call should be

made at 30 days post the last dose of study intervention to determine if any AEs have occurred since the poststudy clinic visit.

## 8.11.4.1 Safety Follow-up Visit

The mandatory Safety Follow-up Visit should be conducted approximately 30 days after the last dose of study intervention or before initiation of a new anticancer treatment, whichever comes first.

All AEs that occur before the Safety Follow-up Visit should be recorded (up to 30 days after the end of treatment).

# 8.11.4.2 Efficacy Follow-up Visits

Participants who complete the protocol-required cycles of study intervention or who discontinue study intervention for a reason other than disease progression will begin Efficacy Follow-up. Participants who discontinue study intervention for reasons other than PD should continue with imaging assessments per the protocol-defined schedule until: (1) radiographic PD is assessed by the investigator, (2) initiation of a new anticancer treatment, (3) death, (4) withdrawal of consent, (5) pregnancy, or (6) study conclusion or early termination, whichever occurs first. Follow-up should be assessed as defined in Section 8.11.4.3, to monitor disease status. Information regarding poststudy anticancer treatment will be collected if new treatment is initiated. Participants who completed all efficacy assessments and/or will not have further efficacy assessments must enter survival follow-up.

# 8.11.4.3 Survival Follow-up Contacts

Participant survival follow-up status will be assessed approximately every 12 weeks to assess for survival status until death, withdrawal of consent, or the end of the study, whichever occurs first.

The first survival follow-up assessment should be scheduled as described below:

- For participants who discontinue treatment intervention and who will not enter Efficacy Follow-up, the first survival follow-up contact will be scheduled 12 weeks after the Discontinuation Visit and/or Safety Follow-up Visit (whichever is last).
- For participants who completed assessments in Efficacy Follow-up, the first survival follow-up contact will be scheduled 12 weeks after the last efficacy assessment follow-up visit has been performed.

# 8.11.5 Poststudy

Participants will be required to return to clinic approximately 30 days after the last dose of study intervention for the poststudy visit. If the poststudy visit occurs less than 30 days after the last dose of study intervention, a subsequent follow-up telephone call should be made at

96

30 days post the last dose of study intervention to determine if any AEs have occurred since the poststudy clinic visit.

#### 8.11.6 Vital Status

To ensure current and complete survival information (vital status) is available at the time of database locks, updated vital status may be requested during the study by the Sponsor. For example, updated vital status may be requested before but not limited to, an eDMC review, interim and/or final analysis. On Sponsor notification, all participants who do not/will not have a scheduled study visit or study contact during the Sponsor-defined time period will be contacted for their vital status.

## 9 STATISTICAL ANALYSIS PLAN

# 9.1 Statistical Analysis Plan Summary

This section outlines the statistical analysis strategies and procedures for the primary and secondary analyses of the study. Exploratory and other nonconfirmatory analyses will be outlined in a separate sSAP.

If, after the study has begun, changes are made to primary and/or secondary objectives, or the statistical methods related to those objectives, then the protocol will be amended (consistent with ICH Guideline E9). Changes to exploratory or other nonconfirmatory analyses made after the protocol has been finalized, but before the conduct of any analyses, will be documented in the sSAP as needed and referenced in the CSR for the study. Post hoc exploratory analyses will be clearly identified in the CSR.

Full details are in the SAP, Section 9.2 through 9.12.

Study Design Overview	Phase 1/Phase 2 study of MK-1088 monotherapy (Arm 1) and MK-1088 in combination with pembrolizumab (Arm 2) in participants with advanced/metastatic solid tumors. The study applies an adjusted mTPI design for dose-finding.	
Intervention Assignment	Participants will be allocated centrally through IVRS by nonrandom assignment.	
Analysis Populations	
 
Safety (Primary): All-Participants-as-Treated
 
PK (Secondary): Per-Protocol
 
Efficacy (Secondary and Exploratory): Full Analysis Set
 
	
Primary Endpoint(s)	
 
Dose-limiting toxicity
 
Adverse event
 
Discontinuing study treatment due to an AE
 
	
Secondary Endpoints	
 
PK parameters including AUC, Cmin, and Cmax
 
ORR based on RECIST 1.1 as assessed by the investigator
 
	

Statistical Methods for Efficacy/ Immunogenicity/ Pharmacokinetic Analyses	
 
ORR based on RECIST 1.1 will be estimated using an exact method based on the binomial distribution (Clopper-Pearson interval).
 
Exploratory efficacy (eg, PFS, OS, and DOR) analyses are documented in the sSAP.
 
PK parameters of study medicines will be summarized by planned visit and time for each dose separately.
 
	
Statistical Methods for Safety Analyses	Summary statistics will be provided for the safety endpoints as appropriate. The pool-adjacent-violators algorithm [Ji Y, Li Y, Bekele BN 2007] will be used to estimate the DLT rates across doses. The estimate of the DLT rate among participants treated at RP2D of MK-1088 and the 90% Bayesian credible intervals for the estimate will be provided for each treatment arm.	
Interim Analyses	No interim analyses are planned. Data will be examined on a continuous basis to allow for dose-finding decisions.	
Multiplicity	No multiplicity adjustment is planned.	
Sample Size and Power	The overall sample size for this study depends on the observed DLT profiles of MK-1088 monotherapy and MK-1088 in combination with pembrolizumab. A target sample size of 80 participants in Part 1 will be used for study planning purposes. Sample size for Part 2 Expansion will be determined once the RP2D is determined.	

# 9.2 Responsibility for Analyses/In-house Blinding

The statistical analyses of the data obtained from this study will be the responsibility of the Clinical Biostatistics department of the Sponsor.

The study is open-label (ie, participants, investigators, and Sponsor personnel will be aware of participant intervention assignment after each participant is enrolled and treatment is assigned). Participants will be allocated by nonrandom assignment.

# 9.3 Hypotheses/Estimation

Objectives and hypotheses of the study are outlined in Section 3.

# 9.4 Analysis Endpoints

# 9.4.1 Efficacy/Immunogenicity/Pharmacokinetics Endpoints

Efficacy endpoints are secondary (ORR) and exploratory (PFS, OS, and DOR) endpoints in this study. The ORR is defined as the percentage of participants who achieve a confirmed CR

PROTOCOL/AMENDMENT NO.: 002-01

or PR per PCWG-modified RECIST 1.1 or RECIST 1.1 as assessed by the investigator. Participants without response assessment will be counted as nonresponders. Details of the analysis plan will be documented in the sSAP for the exploratory objectives. A description of efficacy measures is provided in Section 8.2.

Pharmacokinetic endpoints include plasma concentrations of MK-1088 (and pembrolizumab), as well as derived PK parameters.

# 9.4.2 Safety Endpoints

The primary safety endpoint is the incidence of DLTs. In addition, safety and tolerability will be assessed by clinical review of all relevant parameters including AEs, laboratory tests, and vital signs.

A description of safety measures is provided in Section 8.3.

# 9.5 Analysis Populations

# 9.5.1 Safety Analysis Populations

The APaT population will be used for the analysis of safety data in this study. The APaT population consists of all participants who received at least 1 dose of study intervention. Participants who receive the incorrect study intervention will be summarized according to the actual study intervention they receive.

The DLT-evaluable population includes APaT participants that meet the criteria for DLT evaluability (eg, finished Cycle 1 without a DLT or experienced a DLT in Cycle 1). See Section 5.5 for details. Participants who are DLT nonevaluable will be eligible for inclusion in other analysis populations if they meet the respective criteria.

At least 1 laboratory or vital sign measurement obtained after at least 1 dose of study intervention is required for inclusion in the analysis of each specific parameter. A baseline measurement is also required to assess change from baseline.

Safety data from participants who experienced disease progression in the monotherapy arm and crossed over into the combination arm will be summarized in their initial monotherapy dose group until the time of cross over and will be summarized separately thereafter.

## 9.5.2 Pharmacokinetic Analysis Populations

The per-protocol population will be used for the analysis of PK and target engagement data in this study. The per-protocol population consists of the subset of participants who complied with the protocol sufficiently to ensure that their data will be likely to show the effects of treatment, according to the underlying scientific model. Compliance includes such considerations as exposure to treatment, availability of measurements, and the absence of major protocol violations. Any participants or data values excluded from the analyses will be identified, along with the reasons for exclusion, in the CSR. At the end of the study, all

PROTOCOL/AMENDMENT NO.: 002-01

participants who were compliant with the study procedures and have available data from at least 1 treatment will be included in the per-protocol analysis dataset.

# 9.5.3 Efficacy Analysis Populations

The FAS population will be used for the analyses of efficacy data in this study. It consists of all participants with a screening/baseline scan that showed measurable disease by the investigator's assessment, and who were administered at least 1 dose of study intervention. Participants who receive the incorrect study intervention will be summarized according to the actual study intervention they receive.

Efficacy data from participants who experienced disease progression in the monotherapy arm and crossed over into the combination arm will be summarized in their initial monotherapy dose group until the time of cross over and will be summarized separately thereafter.

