## For metastatic castrate-resistant prostate cancer (mCRPC) only:

- Must have previously received docetaxel, prior treatment with one other chemotherapy is allowed as well as up to 2 second-generation hormonal manipulations.
- Have prostate cancer progression within 6 months before screening, as determined by the investigator, by one of the following:
  - a. PSA progression using local laboratory values as defined by a minimum of 2 rising PSA levels with an interval of  $\geq 1$  week between each assessment where the PSA value at screening should be  $\geq 2$  ng/mL.
  - b. Radiographic disease progression in soft tissue based on PCWG-modified RECIST 1.1 or RECIST 1.1 criteria with or without PSA progression.
  - c. Radiographic disease progression in bone defined as the appearance of 2 or more new bone lesions on bone scan with or without PSA progression.

PRODUCT: MK-1088
PROTOCOL/AMENDMENT NO.: 002-01

Note: Subjects with prostate cancer lesions solely confined to prostate without evidence of metastasis cannot be reliably imaged and therefore are not eligible for study

2. Disease per PCWG-modified RECIST 1.1 for mCRPC or measurable disease per RECIST 1.1 as assessed by the local site investigator/radiology. Target lesions situated in a previously irradiated area are considered measurable if progression has been shown in such lesions.

Note: Lesions situated in the brain are not considered measurable disease and may be considered as nonmeasurable only.

Note: Subjects with prostate cancer lesions solely confined to prostate without evidence of metastasis cannot be reliably imaged and therefore are not eligible for study

For participants with metastatic castrate-resistant prostate cancer:

a. Have PCWG-modified RECIST 1.1 measurable (soft tissue) prostate cancer on CT or MRI scans as assessed by the local site/investigator/radiology

OR

b. Detectable bone metastases by whole body bone scintigraphy as per PCWG guidance (see Section 10.9, Appendix 9)

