#### 3. Documentation of Bone Lesions at Baseline

At screening, individual bone lesions may be recorded as non-target lesions only, and the number of bone lesions should be noted.

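### As written, the Full Analysis Set drops treated mCRPC participants admitted on bone metastases without a measurable lesion from exploratory PFS and OS

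*Combined protocol and SAP*

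**What the plan says.** Four parts of the document bear on this.

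- **Analysis set.** Section 9.5.3 uses the FAS for efficacy data and exempts no endpoint. On membership it says: "It consists of all participants with a screening/baseline scan that showed measurable disease", as judged by the investigator, plus at least one dose. The summary table in Section 9.1 gives the scope as "Efficacy (Secondary and Exploratory): Full Analysis Set".
- **Endpoints.** Section 9.4.1 states: "Efficacy endpoints are secondary (ORR) and exploratory (PFS, OS, and DOR) endpoints in this study". Section 3 defines PFS by progression or death and OS by death, both timed from treatment allocation. Neither definition mentions measurable disease. The objective there concerns PFS and OS in those treated with MK-1088.
- **Eligibility.** Inclusion criterion 2 in Section 5.1.1 asks for "Disease per PCWG-modified RECIST 1.1 for mCRPC or measurable disease per RECIST 1.1". For mCRPC it then offers two routes joined by OR. Route 2a is "Have PCWG-modified RECIST 1.1 measurable (soft tissue) prostate cancer on CT or MRI scans". Route 2b is "Detectable bone metastases by whole body bone scintigraphy as per PCWG guidance".
- **Bone lesions.** Under Appendix 9 (Section 10.9), at screening "individual bone lesions may be recorded as non-target lesions only".

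Section 9.1 also defers methods: "Exploratory and other nonconfirmatory analyses will be outlined in a separate sSAP". That document is not available here.

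**The concern.** A requirement for measurable disease suits a response rate, where tumor shrinkage has to be measured. It has no such role for time to progression or death. Carrying it over to PFS and OS removes people who were eligible, were treated and were followed for exactly these events, and it does so by baseline lesion type.

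PFS and OS would then describe a subset of those treated, while the objective in Section 3 refers to those treated. The participants lost would all have mCRPC, one of the tumors that Section 2.1 cites for an early efficacy signal (it also cites NSCLC and mCRC).

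**Working it through.** The documents give no figure to reproduce. The check is a reading of the text, followed by an illustration of size.

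**Step 1: can a participant be eligible without measurable disease?** Criterion 2 asks mCRPC for disease under PCWG-modified RECIST 1.1 and asks other tumors for measurable disease. Within the mCRPC routes, measurability appears only in 2a, where it is tied to soft tissue. Route 2b is met by bone scintigraphy alone. So yes, on the plain reading.

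**Step 2: could the bone lesions themselves count as measurable?** No. Appendix 9 makes them non-target only, and 2a equates measurable with soft tissue.

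**Step 3: is such a participant in the FAS?** No. Section 9.5.3 requires measurable disease on the baseline scan.

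**Step 4: does the FAS govern PFS and OS?** Yes as written. Section 9.1 assigns it to exploratory efficacy, and Section 9.4.1 lists PFS and OS there.

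**Step 5: are the data collected?** Yes.
- Table 10 (Section 8.2.5) has soft-tissue NED rows, which fit the bone-only case, and an outcome for participants with no target lesions at screening.
- Section 8.2.1 requires bone scintigraphy at every scheduled imaging visit in prostate cancer, and Appendix 9 scores progression from new bone lesions.
- The synopsis follows everyone for survival except those who withdraw consent or are lost to follow-up.

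**Step 6: does the same argument reach ORR?** For bone-only participants, soft tissue is NED. Table 10 then allows five overall results: PD, PDu, NE, Non-CR/Non-PD and NED. None is CR or PR, so leaving these participants out of ORR and DOR is sound.

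**Size (assumed shares, not from the documents).** Number affected = 80 × p × q, where 80 is the Part 1 planning size, p is the mCRPC share and q is the share of those without measurable disease.

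| p | q | Number affected |
|---|---|---|
| 0 | any | 0 |
| 0.10 | 0.20 to 0.50 | 1.6 to 4 |
| 0.25 | 0.20 to 0.50 | 4 to 10 |

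The upper end is 10/80 = 12.5%. These figures show scale only and do not support a severity rating.

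**The case against.** **The sSAP may settle it.** PFS and OS methods are deferred to the sSAP, and Section 9.1 lets changes to exploratory analyses made before any analysis be recorded there. The sponsor could therefore set another population without amending the protocol. This lowers certainty. It does not remove the point, because Sections 9.1 and 9.5.3 already name the population and an sSAP that used a different one would disagree with them.

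**Section 8.2.2 may close the gap.** It tells the investigator to confirm measurable disease on the screening scans, with mCRPC judged by PCWG-modified RECIST 1.1.
- Read strictly, mCRPC needs measurable disease, nobody is lost from the FAS, and the defect becomes an eligibility conflict. That reading leaves 2b with no effect as an alternative and the soft-tissue NED rows of Table 10 with little purpose.
- Read loosely, measurable is shorthand for qualifying under the PCWG rules, and 2b entrants were meant to be in the FAS. That sits badly with the soft-tissue wording in 2a and the non-target rule in Appendix 9.

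What stands is that criterion 2b and Sections 8.2.2 and 9.5.3 do not agree on whether mCRPC needs measurable disease.

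**A reader might infer that ORR is also wrong.** A participant with bone metastases plus nonmeasurable soft tissue could in principle reach CR under Table 10 and not be counted. The documents do not make this an error. Section 9.5.3 deals with the case by excluding it, and limiting ORR to measurable disease is a defensible choice. Such a CR would also need complete soft-tissue response, a bone scan with no lesions, and confirmation on a repeat scan.

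**Conclusion.** The mismatch is real on the plainest reading: criterion 2b admits participants whom the FAS then leaves out of PFS and OS. It rests on two assumptions: that 2b works as a genuine alternative, and that the sSAP follows the population named in Sections 9.1 and 9.5.3.

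Severity is minor. PFS and OS are exploratory, Section 9.8 states that no hypothesis is tested, and the number affected is unknown and may be zero. A reader might go further and infer that dose-finding or safety conclusions are distorted. They are not: the dose rules use DLT counts, and Section 9.5.1 bases safety on all treated participants (APaT) and DLTs on the DLT-evaluable set. Nor do the documents support a claim that a known share of participants is lost or that PFS and OS are biased in a known direction.

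**What to change.** - In Sections 9.1 and 9.5.3, and in the sSAP, extend the FAS for PFS and OS to treated participants whose baseline disease meets inclusion criterion 2, including 2b. This is the smallest repair. Using APaT for PFS and OS would also work, but the text should then say that the baseline-scan condition is dropped as well.
- Keep the measurable-disease set for ORR and DOR if that is intended, and name it as a separate population.
- Reconcile criterion 2b, Section 8.2.2 and Section 9.5.3 so that they agree on whether mCRPC participants need measurable disease.

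The cost is wording only, with no new data, visits or participants. It can go into the amendment that Section 4.1 already requires before Part 2.
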